- Medical history which will be checked on Day-1 is limited to the medical history related to exclusion criteria 1, 2, 3, 6, 8, 9, 10, 11, 13, 14, 15, and 17.
- Serum pregnancy tests at the Screening visit and on Day-1; urine pregnancy tests at the Day 30/Follow-up visit.

- h. HM15912 or placebo will be administered via SC injection into the abdomen on the morning of Day 1 after a minimum 10-hour fast. Subjects will continue fasting through approximately 4 hours postdose. Water consumption will also be limited for 1 hour before dosing and for approximately 2 hours after dosing. After the planned 4-hour post-dose blood sampling (clinical laboratory tests and analysis of citrulline) and testing (12-lead ECG) are performed, subjects will be served lunch by the institution.
- i. Vital signs will be measured twice per day on Day 1 through Day 6 (AM and PM). Vital signs will be measured at predose and 6 hours postdose on Day 1. Vital signs will be measured whenever possible in the morning and afternoon between Day 2 and Day 6. All other assessments will be performed once per day whenever possible. BP and pulse will be measured for 2 consecutive times after a subject has been lying down or sitting to rest \geq 5 minutes, and mean values will be recorded.
- j. Samples for clinical laboratory tests will be collected after at least 12 hours of fasting. If the PK sampling time points are changed, the sampling times for clinical laboratory tests may be adjusted accordingly.
- k. 4, 48 and 72 hours postdose
- l. The 12-lead ECGs will be performed after a subject has been resting supine for \geq 5 minutes. ECGs will be measured in triplicate in the morning during admission. Only for Day 1, however, ECGs will be measured in triplicate predose and 4 hours postdose, and a \pm 30-minute sampling window is allowed for measurement at 4 hours postdose. Triplicate ECGs will be recorded at least 30 seconds apart from each other, not exceeding a time period of 3 minutes for the completion of all 3 ECGs. 12-lead ECGs during the Outpatient visit will be measured once per day whenever possible.
- m. Blood sampling for immunogenicity assessments will be performed only for hospitalized patients after admission on Day-1, Day 10, and Day 30.
- n. Injection site assessments will be performed predose, within 1 hour postdose and at 4 and 12 hours postdose on Day 1, and then between 9:00 AM and 12:00 PM daily from Day 2 through Day 7.

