3.2. Endpoints

3.2.1. Primary Endpoints

- General safety variables: Adverse event (AE) assessments, clinical laboratory tests (hematology, clinical chemistry, coagulation and urinalysis), vital signs (blood pressure [BP], pulse, tympanic temperature and respiratory rate [RR]), 12-lead electrocardiogram (ECG), physical examinations
- Specific safety variables: Injection site assessments, immunogenicity assessments (ADA, NAb, anti-PEG) (performed only if analysis is necessary)

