3.4. Dose Escalation and Study Stopping Criteria

Dose escalation will be stopped if 1 of the following conditions applies:

- Death of a subject in 1 cohort, at any time, that is considered to be related to the IP, judged by the Principal Investigator
- One or more of the subjects in 1 cohort have experienced serious AE that is considered to be related to the IP, judged by the Principal Investigator.
- Two or more of the subjects in 1 cohort have experienced severe AE that is considered to be related to the IP, judged by the Principal Investigator.
- Two or more of the subjects in 1 cohort have experienced moderate AEs that persist for more than 7 days and are considered to be related to the IP, judged by the Principal Investigator.
- Two or more of the subjects in 1 cohort develop similar clinically significant laboratory, significant ECG or vital sign abnormalities, or severe AEs in the same organ class,

indicating dose-limiting intolerance. Dose escalation may proceed if after review of the data by the Principal Investigator and discussion with the Sponsor, it is concluded that the events are not drug related.

- It is determined that the limit of safety and/or tolerability has been reached. Decision will be made between the Sponsor and the Principal Investigator.

If any delayed reactions occur in subjects administered HM15912 during this study, the Principal Investigator will immediately stop the administration and take appropriate medical measures. If delayed reactions are suspected to be drug hypersensitivity reactions, appropriate medical measures will be taken in accordance with 7.9. Handling of Hypersensitivity Reactions. If Principal Investigator and Sponsor discuss and agree that administering HM15912 to other subjects is an unacceptable risk, they may stop the study as below.

The Principal Investigator and the Sponsor may stop the clinical study after an appropriate discussion if conditions or events including, but not limited to, the following occur during the study. A sufficient written statement on the reason for stopping the study will be submitted to the IRB.

- If clear risks or unacceptable risks are found in the subjects enrolled in this clinical study
- If the Sponsor decides to postpone or stop development of the IP

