6.2.3. Vital Signs

Vital signs will be assessed at the time points specified in the Schedule of Assessments ([Table 1-1](#) and [1-2](#)). The following vital signs will be measured:

- Blood pressure (systolic and diastolic [mmHg])
- Pulse (bpm)
- Tympanic temperature (°C)
- Respiratory rate (breaths per minute)

BP and pulse will be measured for 2 consecutive times after a subject has been lying down or sitting to rest \geq 5 minutes, and mean values will be recorded.

6.2.4. 12-lead Electrocardiograms

12-lead ECGs will be performed at the time points specified in the Schedule of Assessments ([Table 1-1](#) and [1-2](#)). ECGs will be measured 3 times repeatedly predose and 4 hours postdose each on Day 1 only. A deviation of \pm 30 minutes from the collection time points is allowed in case of measurement 4 hours after dosing.

The 12-lead ECGs will be performed after a subject has been resting supine for \geq 5 minutes. Triplicate ECGs will be recorded at least 30 seconds apart from each other, not exceeding a time period of 3 minutes for the completion of all 3 ECGs. The following ECG parameters will be collected: Ventricular rate, PR interval, QRS interval, RR interval, QT interval and QT interval corrected for heart rate (QTc) (QTc using Bazett's correction [QTcB] and QTcF).

All ECGs must be evaluated by the Investigator for the presence of abnormalities. If any clinically significant abnormality is observed, it must be recorded as an AE.

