8.10. Interim Analyses

No formal interim analysis is planned. However, available blinded safety and tolerability (including PK/PD data if available) from each cohort (Day-1 to Day 17) will be evaluated in a dose escalation review meeting by the Principal Investigator and the Sponsor. The data review will take place before dose escalation can proceed. Screening for the next cohort may be conducted even before proceeding to the next cohort is determined, but the IP should be administered after proceeding to the next cohort is determined.

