**Table 4-2. Schedule of Assessments (Cohort 4, 5)**

Visit	Visit 1 Screening	Visit 2 Inpatient Treatment Period							Visit 3 Out patient a	Visit 4 Out patient a	Visit 5 Out patient a	Visit 6 Out patient a	Visit 7 Follow- up b	
		-1 Outpa- tient	-1 Inpa- tient	1	2	3	4	5						
Day	-28 ~ -2								8 (±4 hours)	10 (±1 day)	17 (±1 day)	30 (±3 days)	44 (±3 days)	
Informed consent	X													
Inclusion/exclusion criteria	X	X c												
Demographic data	X													
Height d , BMI e	X	X							X		X	X	X	X
Body weight d	X	X							X		X	X	X	X
Medical history	X	X f												
Prior/concomitant medications	X	X		X	X	X	X	X	X		X	X	X	X
Pregnancy test (all females) g	X	X												X
Serum FSH (postmenopausal females only)	X													
Urine drugs of abuse and alcohol screening s	X	X								X	X	X	X	X
Viral serology	X													
Check-in			X											
Check-out									X					
Outpatient	X	X								X	X	X	X	X
Randomization		X												
Standardized meals			X	X h	X	X	X	X						
IP administration h				X										
Adverse event assessments	X	X	X	X	X	X	X	X	X	X	X	X	X	X

Visit	Visit 1 Screening	Visit 2 Inpatient Treatment Period									Visit 3 Out patient a	Visit 4 Out patient a	Visit 5 Out patient a	Visit 6 Out patient a	Visit 7 Follow- up b
		-1 Outpa- tient	-1 Inpa- tient	1	2	3	4	5	6	7					
Day	-28 ~ -2														
Vital signs (BP, pulse, tympanic temperature, RR) i	X	X		X i	X	X	X	X	X	X					
Clinical laboratory tests (hematology, chemistry, coagulation, urinalysis) j	X	X		X k			X k			X			X	X	X
12-lead ECG l	X	X		X l	X	X	X			X	X	X	X	X	X
Immune response assessments (ADA, NAb, anti-PEG)			X m										X		X
Injection site assessments n				X	X	X	X	X	X						
Physical examinations	X	X		X	X	X	X	X	X	X	X	X	X	X	X
[REDACTED]				[REDACTED]	[REDACTED]	[REDACTED]	[REDACTED]	[REDACTED]	[REDACTED]	[REDACTED]	[REDACTED]	[REDACTED]	[REDACTED]	[REDACTED]	[REDACTED]
[REDACTED]				[REDACTED]	[REDACTED]	[REDACTED]	[REDACTED]	[REDACTED]	[REDACTED]	[REDACTED]	[REDACTED]	[REDACTED]	[REDACTED]	[REDACTED]	[REDACTED]
GIP, GLP-1, C-peptide, glucagon, insulin q				X			X			X			X	X	
IGF-1 and KGF r				X			X			X			X	X	

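### No vital signs are scheduled after discharge, so blood pressure, temperature and respiratory rate have no planned reading in the 10–11 days up to Day 17, the data point for the escalation review

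*Protocol*

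**What the plan says.** Section 6.2.3 of the protocol sets no times of its own: "Vital signs will be assessed at the time points specified in the Schedule of Assessments". The schedule is therefore the only source.

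Note i, worded the same way in Protocol Tables 1-1 and 1-2 and in both SAP appendix copies, gives the inpatient frequency: "Vital signs will be measured twice per day on Day 1 through Day 6 (AM and PM". It then adds: "All other assessments will be performed once per day whenever possible". It names no outpatient or follow-up visit. Note l to the same tables does name them for ECG: "12-lead ECGs during the Outpatient visit will be measured once per day whenever possible".

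The plan relies on vital signs in three places:

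- Section 3.2.1 lists among the primary endpoints "vital signs (blood pressure [BP], pulse, tympanic temperature and respiratory rate [RR".
- Section 3.4 stops escalation if two or more subjects in a cohort develop similar clinically significant findings, among them "significant ECG or vital sign abnormalities".
- Section 8.10 says that available blinded safety data "from each cohort (Day-1 to Day 17) will be evaluated in a dose escalation review meeting". SAP section 7.6 lists blood pressure, pulse, temperature, respiratory rate and body weight for that meeting.

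Section 8.11 also counts vital signs among the measures by which safety is judged over the whole study.

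**The concern.** Discharge is on Day 7. The escalation review takes place after at least six subjects in a cohort have completed Day 17. If nothing is measured after discharge, more than half of the review window has no scheduled blood pressure, temperature or respiratory rate. The vital-sign limb of the stopping rule then has nothing planned to act on in that period.

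The product makes the later period relevant. It is first-in-human and designed for a prolonged half-life (section 1.1). Section 1.3 lists pyrexia and fluid overload among the expected effects. Section 7.8.2 anticipates delayed hypersensitivity with fever within weeks of dosing. An asymptomatic change in blood pressure, temperature or respiratory rate after Day 6 or 7 would have no scheduled measurement to reveal it.

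The gap also reaches subjects who leave early, because the termination visit in section 7.6 repeats the Follow-up procedures, and those include no vital signs.

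**Working it through.** The plan states no figure on this point, so there is none to reproduce. The check is a count of schedule cells followed by subtraction of study days.

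**Step 1. Marks in the vital-signs row.** The row is headed "Vital signs (BP, pulse, tympanic temperature, RR" in each copy.

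| Copy | Marks in row | Inpatient days marked | Post-discharge cells marked |
|---|---|---|---|
| Protocol Table 1-1 (Cohorts 1–3) | 8 | Days 1–6 | 0 of 3 |
| Protocol Table 1-2 (Cohorts 4–5) | 8 | six inpatient cells | 0 of 5 |
| SAP appendix Table 3-1 (Cohorts 1–3) | 7 | Days 1–5 | 0 of 3 |
| SAP appendix Table 4-2 (Cohorts 4–5) | 9 | Days 1–7 | 0 of 5 |

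Total after discharge: 3 + 5 + 3 + 5 = 16 cells, none marked. The adverse-event, ECG and physical-examination rows do carry marks at these visits.

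**Step 2. Could marks have been lost from the tables?** In the text form of these PDF tables some cells have shifted or dropped. The injection-site row, for example, shows 6 of its 7 days in both SAP copies, and Protocol Table 1-2 lacks an inpatient column. Two checks address this.

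- *Mark count.* Screening (1) + Day -1 (1) + Days 1–6 from note i (6) = 8. Both protocol tables show exactly 8 marks, so no displaced mark is left over that could belong to an outpatient visit.
- *Rows whose outpatient visits are fixed elsewhere.* These are laboratory tests (Tables 3-1 and 3-2), immunogenicity (note m), the GIP panel (note q) and IGF-1/KGF (note r). Expected outpatient marks: laboratory 2 + 3 + 2 + 3 = 10 over four copies; each of the other three rows 2 × 3 = 6 over the three copies where it can be read. Total 10 + 6 + 6 + 6 = 28. Every row has its full count (8 of 8, 3 of 3, 5 of 5, 5 of 5), so all 28 are present, although some sit in the wrong column. In the SAP copies the laboratory row matches Tables 3-1 and 3-2 column by column.

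**Step 3. Last inpatient reading.** Note i fixes Day 6. SAP Table 4-2 also marks Day 7, and note i's Day 6 limit applies only to the twice-daily frequency. Both days are carried forward. The Day 5 ending in SAP Table 3-1 is set aside because note i requires Day 6.

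**Step 4. Time without a scheduled reading** (visit day minus last reading day).

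| To | Last reading Day 7 | Last reading Day 6 |
|---|---|---|
| Day 17 | 17 − 7 = 10 days | 17 − 6 = 11 days |
| Day 30 (last visit, Cohorts 1–3) | 30 − 7 = 23 days | 30 − 6 = 24 days |
| Day 44 (last visit, Cohorts 4–5) | 44 − 7 = 37 days | 44 − 6 = 38 days |

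With the ±1-day window on Day 17, the first row runs from 16 − 7 = 9 to 18 − 6 = 12 days. The visits inside the review window without vital signs are Days 10 and 17 in Cohorts 1–3, and Days 8, 10 and 17 in Cohorts 4–5.

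**Step 5. Effect of adding readings.** With vital signs at Days 10 and 17, the longest nominal interval before the review becomes 17 − 10 = 7 days, and a Day 17 reading exists.

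**The case against.** The strongest reply is that this is unclear drafting and not a gap in design. The second sentence quoted from note i can be read as one reading per day on other occasions. Section 7.4 says outpatient visits include safety assessments, and section 8.11 speaks of vital signs over the whole study. This shows that outpatient readings may have been intended. It does not schedule them: none of these texts names a vital-sign visit, and section 6.2.3 sends the reader back to a blank row. Section 8.11 sharpens the point, because the schedule does not deliver what it describes.

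A second reply is that the tables are too unreliable to prove a blank. The laboratory row in Protocol Table 1-1 appears blank at Day 17, where Table 3-1 requires chemistry. The concomitant-medication row for Cohorts 4–5 is marked at Day 8 in one copy and not in the other. A single blank cell therefore proves little, and the 28 of 28 figure rests on row totals, not positions. Sixteen consistent blanks, with no spare mark in either protocol table, are another matter.

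The third reply concerns cover from other assessments. Adverse-event questioning, physical examination, ECG ventricular rate, body weight and the Day 17 laboratory panel (with hs-CRP, white cells and eosinophils) all continue, and section 6.2.7 lets the investigator add evaluations. The delayed reactions in section 7.8.2 would usually cause symptoms. This stands, and it is why the concern is limited to asymptomatic changes in blood pressure, temperature and respiratory rate.

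**Conclusion.** The concern holds. Followed as written, the plan has no scheduled blood pressure, temperature or respiratory rate after Day 6 or 7. That is nominally 10–11 days up to Day 17 (9–12 with the visit window), inside the period the escalation review is meant to cover. The review meeting comes after Day 17, so the time from the last reading to the decision itself is longer still.

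The conclusion rests on the blank cells being real, which the agreement of four copies and the mark counts support; a look at the original table pages would settle it. The one-day range reflects the copies' disagreement about Day 7.

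The documents give no basis for estimating how often an escalation decision would differ, and none is claimed. This is a worthwhile safety amendment and not a threat to the validity of the study. If outpatient readings were always intended, the same clarification is still needed.

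**What to change.** - In Protocol Tables 1-1 and 1-2, mark the existing set (blood pressure, pulse, tympanic temperature, respiratory rate) once at Days 10, 17 and 30 for Cohorts 1–3, and once at Days 8, 10, 17, 30 and 44 for Cohorts 4–5.
- Amend note i in both tables to say that vital signs are taken once at each Outpatient and Follow-up visit, as note l does for ECG, and to state whether Day 7 is included.
- Make the same changes in the SAP appendix copies. SAP section 7.6 needs no change, since it already lists these variables.

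The cost is an amendment to a table row and a footnote, and a few minutes at visits subjects already attend. It needs no new visit or blood draw.

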3. OVERALL DESIGN AND PLAN OF THE STUDY

3.1. Overview

This is a double-blind, randomized, placebo-controlled, single ascending dose (SAD) study to assess the safety, tolerability, PK and PD of the SC administration of HM15912 in healthy Korean subjects.

The study will be conducted in approximately 5 sequential dosing cohorts, enrolling 8 subjects per cohort. Subjects will be randomized to HM15912 or placebo in a ratio of 6:2 (6 active, 2 placebo). When necessary, one dosing cohort may be added or removed.

Each cohort will be divided in 2 blocks in this FiH study in order to implement the sentinel dosing approach. Within each cohort, the first block will consist of 2 sentinel subjects; 1 subject will receive HM15912, and 1 subject will receive matched placebo. The second block will consist of 6 subjects randomized to receive HM15912 (n = 5) or matched placebo (n = 1). Individual subjects in the second block will be dosed at least 24 hours after the first block when safety and tolerability are found to be satisfactory by the Principal Investigator.

Following an overnight fast of at least 10 hours, each subject will receive a single dose of either HM15912 or matched placebo-administered SC in the abdomen on the morning (8:00 AM - 10:00 AM) of Day 1. Subjects will continue fasting through approximately 4 hours postdose. Water intake is also limited for approximately 1 hour before dosing and approximately 2 hours after dosing.

The planned maximum dose of HM15912 is 1.5 mg/kg; however, higher doses may be administered if safety is confirmed in previous cohorts. If dose is escalated to 1.5 mg/kg or above, MFDS approval will be obtained. After at least 6 subjects (HM15912, n ≥ 4) in each cohort have completed assessments through at least Day 17, blinded safety data will be reviewed and a dose decision/dose escalation decision for the subsequent cohort will be made by the Principal Investigator and the Sponsor. If there are PK/PD data obtained from the preceding or current cohorts, the PK/PD data will be reviewed as well when necessary. Escalation will only proceed if safety and tolerability data related to the dose of the prior cohort are verified. Determination of whether to proceed to the next cohort will be made by the Principal Investigator and the Sponsor, and changes in the dose and the number of cohorts will be approved by the MFDS and the IRB.

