3.3. Rationale for the Study Design

This study evaluates the safety, tolerability, PK and PD of single ascending doses of HM15912 administered via SC injection. This study was designed to minimize bias and to obtain reference data (i.e., data from placebo-treated subjects) which will aid in the interpretation of results through double blind and placebo control.

For this FiH study, sentinel dosing will be utilized for each cohort. This will minimize the number of subjects affected by rapid side effects after HM15912 administration. The Principal Investigator and the Sponsor will review available blinded safety and tolerability data after each cohort to determine the next dose and then decide whether the dose escalation should be stopped or whether the dose should be increased/decreased in the subsequent cohort. If PK/PD data have been obtained, they can be used for reference. This is not mandatory, however.

The planned safety assessments that will be performed during the study are measures for ensuring the safety of subjects during a clinical trial. The PK sampling schedule is considered appropriate given the information obtained from the nonclinical study results of HM15912. The rationale for dose selection is discussed in Section 5.2.

Based on the in vivo effect of endogenous GLP-2, the exogenous administration of HM15912, a GLP-2 analogue, is expected to expand the mucous epithelium of the small intestine and colon resulting from the proliferation of crypt cells¹. Plasma citrulline is a nonprotein amino acid that is mostly synthesized in the small intestine cells, and is well-known as a noninvasive plasma biomarker for intestinal cell mass². Apolipoprotein AIV is also mostly synthesized in the small intestine cells, and previous studies have shown the correlation between apolipoprotein AIV and plasma citrulline levels³. Therefore, effect of HM15912 on expansion of the intestinal mucous membrane will be explored by measuring plasma citrulline after HM15912 administration. The serum proteins, albumin and prealbumin, and serum lipid panel will also be evaluated to observe changes in nutrient status of subjects resulting from expansion of the intestinal mucous membrane⁴.

GLP-2 affects the pancreas and is involved in the secretion of glucagon and maintenance of glucose homeostasis¹. These pancreatic hormones are balanced in a physiological condition, and this study will explore the effect of GLP-2 administration on the homeostasis.

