6.2.5. Injection Site Assessments

Injection site assessments will be performed at the time points specified in the Schedule of Assessments ([Table 1-1](#) and [1-2](#)).

After injection of the study drug, the injection site will be marked with a pen. Injection site assessments will be performed predose, within 1 hour postdose and at 4 and 12 hours postdose on Day 1, and then once per day between 9:00 AM and 12:00 PM from Day 2 through Day 7. A deviation of \pm 30 minutes from the assessment time points is allowed in case of measurements 4 and 12 hours after dosing.

It will be checked whether the injection site mark is well-maintained during injection site assessments. If the pen mark fades, it will be marked again to show clearly the injection site. If patients who show injection site reactions are discharged, they will be separately guided to maintain their injection site marks.

Erythema and edema among the local reactions of injection sites will be evaluated quantitatively using the Draize scale described below. If an injection site reaction like pain on palpation, itching, erythema, edema, induration is observed, it must be recorded as an AE. Note, however, that pain during injection is a natural response, so it is not considered an AE. Local reactions of the injection sites will be evaluated and recorded by one Investigator using the following scale:

Erythema will be evaluated as follows:

- 0 – No erythema
- 1 – Very slight erythema (barely perceptible)
- 2 – Well-defined erythema
- 3 – Moderate to severe erythema
- 4 – Severe erythema (beet redness) to slight eschar formations (injuries in depth)

Edema will be evaluated as follows:

- 0 – No edema
- 1 – Very slight edema (barely perceptible)
- 2 – Slight edema (edges of area well defined by definite raising)
- 3 – Moderate edema (raised approximately 1 mm)
- 4 – Severe edema (raised more than 1 mm and extending beyond the area of exposure)

For the irritation assessment, all irritation events will be documented as AEs. If AEs occur, the diameter of affected sites will be measured in centimeters (cm) and the condition of the injection sites will be recorded. In case of clinically significant injection site reactions, subjects may undergo a dermatological consultation and/or cutaneous biopsies for further histological examination of the injection site reaction.

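### Day 1 vital signs are scheduled only at predose and 6 h in a first-in-human study; adding readings at 1 h, 4 h and 12 h is a cheap improvement

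*Protocol*

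**What the plan says.** Note i to Protocol Table 1-1 (Cohorts 1-3) and Table 1-2 (Cohorts 4-5) gives the Day 1 times: "Vital signs will be measured at predose and 6 hours postdose on Day 1". The same note sets two readings a day from Day 1 to Day 6, so predose and 6 h are the whole Day 1 set. From the next day it says: "Vital signs will be measured whenever possible in the morning and afternoon between Day 2 and Day 6", with no clock time. The two schedules in the SAP appendix repeat the note. Protocol 6.2.3 defines vital signs as blood pressure, pulse, tympanic temperature and respiratory rate, and refers back to the tables for timing.

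Staff already see each subject on Day 1 for other reasons. Note n says: "Injection site assessments will be performed predose, within 1 hour postdose and at 4 and 12 hours postdose on Day 1". A triplicate ECG and a laboratory draw also fall at 4 h, before lunch.

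On sentinel dosing, Protocol 3.1 says of the six non-sentinel participants in a cohort that they "will be dosed at least 24 hours after the first block when safety and tolerability are found to be satisfactory by the Principal Investigator". Protocol 3.3 gives the reason: "This will minimize the number of subjects affected by rapid side effects after HM15912 administration".

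**The concern.** The design guards against rapid reactions, yet for 6 h after dosing it schedules no blood pressure, temperature or respiratory rate. Protocol 1.3 lists hypersensitivity, pyrexia and fluid overload among the expected effects, and all three measurements are relevant to these. The injection site, by contrast, is checked within the first hour and again at 4 h.

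A change that begins after dosing and settles before 6 h, without symptoms that prompt an unscheduled check, would leave no planned record. Vital signs are part of the primary endpoint (Protocol 3.2.1). They are also among the data on which the investigator can judge the two sentinels before the second block is dosed.

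**Working it through.** **Is there a scheduled reading elsewhere before 6 h?**

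- Protocol 6.2.3 only points back to the tables.
- Protocol 6.2.4: the 4-h ECG records ventricular rate and intervals. Its RR interval is the cardiac R-R interval, not respiratory rate. Heart rate is therefore covered at 4 h; the other vital signs are not.
- Protocol 6.2.7: the physical examination covers general appearance and body systems. It lists no vital signs, and the tables give it no Day 1 clock time.
- Protocol 7.8.1: blood-pressure and respiratory monitoring is optional and applies when anaphylaxis is suspected.

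So there is none.

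**Gaps in the first 6 h.** Dosing is time 0, and the predose reading is taken as 0 h. The gap is the difference between consecutive scheduled times.

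| Schedule (h) | Gaps (h) | Longest (h) |
|---|---|---|
| Blood pressure now: 0, 6 | 6 | 6 |
| With 1 h and 4 h: 0, 1, 4, 6 | 1, 3, 2 | 3 |
| Same, 1 h taken 15 min early and 4 h taken 30 min late: 0, 0.75, 4.5, 6 | 0.75, 3.75, 1.5 | 3.75 |
| Heart rate now (with ECG): 0, 4, 6 | 4, 2 | 4 |
| Heart rate with the change: 0, 1, 4, 6 | 1, 3, 2 | 3 |

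The predose time for vital signs is not stated. If the reading were up to 2 h before dosing (assumption), the present gap would be 6 to 8 h. The proposed longest gap would remain 3 h, because the first gap would be at most 1 + 2 = 3 h.

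**From 6 h to Day 2.** Dosing is "on the morning (8:00 AM - 10:00 AM) of Day 1", which puts the 6-h reading at 2:00 to 4:00 PM. If the Day 2 reading is at 8:00 AM (assumption), it falls 22 to 24 h after dosing.

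- Now: 22 − 6 = 16 h to 24 − 6 = 18 h.
- With only 1 h and 4 h added: unchanged at 16 to 18 h.
- With 12 h added: 22 − 12 = 10 h to 24 − 12 = 12 h. If that reading is 30 minutes early, the upper end is 24 − 11.5 = 12.5 h.

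**Fixed-time post-dose readings per sentinel before the second block can be dosed.** Now 1 (6 h); with the change 4 (1, 4, 6 and 12 h). The Day 2 reading is not counted because it has no clock time.

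**Load.** 3 sets × 8 subjects = 24 per cohort; 24 × 5 cohorts = 120. If only Cohorts 4 and 5 remained (assumption): 3 × 16 = 48 sets, with 2 × 2 = 4 placebo subjects at the new times instead of 2 × 5 = 10.

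**The case against.** The documents agree with one another on this schedule, and it breaks no rule in them. Subjects are inpatients with adverse-event assessment, and unscheduled checks are allowed. Acute hypersensitivity would normally show symptoms, for which Protocol 7.8.1 provides. HM15912 is built for a long half-life (Protocol 1.1). If exposure peaks after Day 1, early readings fall when exposure is low, and vital signs are already taken twice daily on Days 2 to 6. The documents give no Tmax, and the PK sampling times are blacked out, so this cannot be settled. These arguments stand as limits on the benefit. They do not remove the gap, because hypersensitivity need not follow exposure and there was no previous human experience.

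An early gap measured only to 6 h also flatters the 1-h and 4-h readings, since they leave the longer stretch before second-block dosing untouched. That is correct, and it is why the 12-h reading belongs in the main change.

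Two stronger readings are tempting. A reader might infer that the stopping criteria would miss early toxicity, because one of them reads "Two or more of the subjects in 1 cohort develop similar clinically significant laboratory, significant ECG or vital sign abnormalities". That criterion goes on to require that the findings point to dose-limiting intolerance. A brief, symptom-free change is an unlikely trigger, so no claim about the stopping rule is made. A reader might also infer that lunch distorts the 6-h value. The documents give no basis for the size of such an effect, and none is claimed.

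**Conclusion.** The gap is real: there is no scheduled blood pressure, temperature or respiratory rate in the first 6 h after dosing, in any cohort. It concerns scheduled readings only. The plan does not leave subjects unobserved, and the documents would not support saying so. Nor is it an inconsistency or a breach of the protocol.

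The change would bring the longest blood-pressure gap in the first 6 h from 6 h to 3 h nominally, and the stretch to Day 2 from 16-18 h to about 10-12 h. The first figure takes predose as 0 h and rises to 3.75 h at the limits of the suggested windows. The second assumes an 8:00 AM reading on Day 2. What this would prevent or reveal cannot be quantified, because the documents give no likelihood of an early transient change. It is worth considering because it is cheap, and it is a low-severity point.

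**What to change.** For cohorts still to be dosed, amend note i in Protocol Tables 1-1 and 1-2, and its copies in the SAP appendix, to: *Day 1 vital signs at predose and at 1 h, 4 h (with the ECG, before lunch), 6 h and 12 h postdose.* Give windows, for example ±15 min at 1 h and ±30 min at 4 h and 12 h. The latter matches the injection-site tolerance in Protocol 6.2.5, where a 30-minute deviation "from the assessment time points is allowed in case of measurements 4 and 12 hours after dosing". Keep the twice-daily readings on Days 2 to 6. Show the new times in the outputs of SAP 6.2.3 and 7.6.

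Leave the first injection-site check as within 1 hour. Moving it to exactly 1 hour would loosen an existing safety check. The two can share a contact when the vital signs are read at or just before 1 h.

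Cost: three extra sets per subject, 24 per cohort and at most 120. The 5-minute rest is new at 1 h and 12 h; at 4 h the ECG already requires it. No new visit or type of procedure is needed. The amendment needs IRB approval (Protocol 10.8), and the eCRF and SAP need updating. Protocol 3.1 requires MFDS approval as well for changed PK, laboratory and PD times. Vital signs are not on that list, so the sponsor should confirm whether it applies.

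How many cohorts remain to be dosed is not known from the documents. If only Cohorts 4 and 5 do, the load is 48 sets, the new times have 4 placebo subjects, and they cannot be compared with Cohorts 1-3.
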